4.1 Study design

The current study will be an open label randomized trial using a two–arm design with 1:1 allocation ratio. The participating centre is the Centre for Reproductive Medicine, Universitair Ziekenhuis Brussel, Belgium. PGT patients who fulfil the inclusion criteria of the study will be recruited from this centre. The aim of the current study is to investigate the effect of the above-mentioned treatment regimen (NC and HRT) in FET cycles on miscarriage rate.

4.2 Selection of study population

The study population consists of all PGT patients who fulfil the following inclusion criteria:

- Age between 18 and 42 years
- BMI under 35 kg/m²
- Regular menstrual cycle pattern (i.e. 24-35 days cycle)
- First, second and third ICSI-PGT cycle
- First frozen embryo transfer cycle following a fresh ICSI-PGT attempt
- PGT with trophectoderm biopsy on day 5 of embryonic development
- Signed informed consent

The exclusion criteria involve:

- Oligo-amenorrhea
- Age above 43 years
- BMI above 35
- Contraindications for the use of hormonal replacement therapy

4.3 Screening

On the first consultation, the treating physician will inform the eligible PGT patients about the study. Patients willing to participate and fulfilling the inclusion criteria will be randomized to one of the two treatment arms following the fresh ICSI cycle if non-affected embryos are available. Informed consent forms will be signed either on the first day of the following menstrual cycle or on the moment of frozen-warmed embryo transfer.

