4.4 Randomization

Patients will be randomized to either natural cycle frozen-thawed embryo transfer (group A), or hormonal replacement therapy cycle frozen-thawed embryo transfer (group B). As mentioned above, patients will only be randomized if they meet the complete eligibility criteria. Randomization will be ensured using a computer-generated randomization list and allocation concealment by the use of sealed opaque envelopes in the centre (physician will neither have access to the randomization list nor to the envelopes, which will be opened by study nurses involved in the study).

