4.5 Interventions

- Natural cycle FET (Group A)

Patients are asked to perform a blood sample, with evaluation of serum estradiol (E2), progesterone (P), luteinizing hormone (LH) and follicle stimulating hormone (FSH), on the first or second day of the menstrual cycle (day 1 is considered as the first day of fresh red blood loss before 12AM). If these serum hormonal values are considered basal for the beginning of the follicular phase, patients are asked to come back on day 10 to 12 of the cycle for blood sample and transvaginal ultrasound scan

in order to assess follicular growth. Depending on the values on day 1 or 2, the physician performing the daily monitoring can decide to perform an earlier examination if necessary.

The timing of ovulation is determined based on a combination of ultrasonography features (the presence of a dominant follicle and adequate endometrium) and endocrine hormonal values in serum blood samples. Ovulation is generally defined as an, at least, 180% increase of LH compared to the mean level in the previous 24h (Frydman et al., 1982).

Frozen-warmed embryo transfer will take place six days following the spontaneous LH surge. Another blood sample will be performed 12 days after embryo transfer measuring human chorionic gonadotrophin (hCG), progesterone and estradiol in order to assess the outcome of the FET cycle.

- Hormonal replacement therapy cycle FET (Group B)

Patients are asked to perform a blood sample, with evaluation of serum estradiol (E2), progesterone (P), luteinizing hormone (LH) and follicle stimulating hormone (FSH) on the first or second day of the menstrual cycle (day 1 is considered as the first day of fresh red blood loss before 12AM). If these values are considered basal for the beginning of the follicular phase, estrogen supplementation (Estradiol valerate, Progynova® 3x2mg/day) is started to induce proliferation of the endometrium. Blood sample and transvaginal ultrasound are thereafter performed ten to fourteen days later. If the endometrium is considered adequate (generally considered if triple line and above 6,5 mm thickness)(Liu et al., 2018), embryo transfer is scheduled on the sixth day of progesterone (vaginal micronized progesterone, Utrogestan® 2x200mg twice a day) supplementation.

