5.2 Sample size calculation

Sample size calculation was performed using internal data of our centre considering early miscarriage rates (defined as miscarriage before 8 weeks of gestation). We observed in our PGT population in 2017 an early miscarriage rate per started FET cycle of 9,9% in the natural cycle group compared to 18,4% in the group using HRT.

Based on these results, 522 patients are required (261 in each treatment arm) to have an 80% chance of detecting, as significant at the 5% level, an increase in the primary outcome measure (early pregnancy loss) from 9,9% in the NC group to 18,4% in the HRT group.

7. Ethical consideration

The protocol will be submitted to the local Ethics Committee of UZ Brussel. Strict confidentiality of all personal and research data will be ensured. The recruiting centre will be required to sign a clinical trial agreement document detailing their commitment towards complying with the relevant laws, regulations, codes of practice and obligations to publication. There are no conflicts of interest.

No specific reimbursement will be given to patients participating in the study.

8. References

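### Women are allocated before the day 1-2 basal-hormone check, and possibly before signing consent; opening the envelope after both would be a cheap improvement

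*Protocol*

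**What the plan says.** All references are to the protocol.

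- **Timing of allocation (4.3 Screening).** Women who are willing and meet the inclusion criteria "will be randomized to one of the two treatment arms following the fresh ICSI cycle if non-affected embryos are available". No exact day is given.
- **Condition for allocation (4.4 Randomization).** The section states that "patients will only be randomized if they meet the complete eligibility criteria". The criteria in 4.2 contain no hormone result.
- **Blinding (4.1 Study design).** "The current study will be an open label randomized trial using a two–arm design with 1:1 allocation ratio".
- **Hormone check, NC arm (4.5 Interventions).** "If these serum hormonal values are considered basal for the beginning of the follicular phase, patients are asked to come back on day 10"; the window for this visit closes on day 12. The physician may also bring an examination forward, depending on the day 1-2 values.
- **Hormone check, HRT arm (4.5 Interventions).** "If these values are considered basal for the beginning of the follicular phase, estrogen supplementation" is started. Section 5 (Treatment) repeats this condition. Neither arm has a numeric limit, or a stated path for a woman whose values are not basal.
- **Consent (4.2 and 4.3).** Signed consent is an inclusion criterion, but the form is signed on the first day of the menstrual cycle after the fresh attempt, or at the time of transfer.
- **Planning rates (5.2 Sample size calculation).** The section uses an "early miscarriage rate per started FET cycle of 9,9% in the natural cycle group" against 18.4% with HRT, and applies these rates to 522 patients, 261 per arm. It does not define a started cycle and makes no allowance for women who are randomised and do not start one.

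**The concern.** The check on day 1 or 2 conditions what happens next in both arms, but it is made after allocation and by staff who can know the arm. The laboratory values are objective. Whether they count as basal is a judgement, and the protocol fixes no limit for it. A doubtful result holds back drug treatment in one arm and affects only the visit schedule in the other, so the same result may be handled differently in the two arms.

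The consent rule opens a second route. A woman allocated after the fresh cycle can learn her arm before she signs, and then decline or not return.

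Either route can lose women between allocation and cycle start, and the loss may differ by arm. If these women are left out of the analysis, the comparison is no longer between the groups as randomised. If they are kept, they cannot have a miscarriage in the trial cycle, so they count as non-events and shift the event rate of their arm. An analysis plan can say who is counted, but it cannot change when the envelope is opened.

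**Working it through.** **1. Order of events.**

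| Step | Where | Arm known? |
|---|---|---|
| Eligibility, non-affected embryos available | 4.2, 4.3 | No |
| Envelope opened | 4.3, 4.4 | Becomes known |
| Consent signed (day 1 of next cycle, or at transfer) | 4.3 | Possibly yes |
| Day 1-2 hormones judged basal or not | 4.5, within each arm | Yes |
| Estrogen start (HRT) or return visit (NC) | 4.5 | Yes |

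The order is read from the sections together, because no randomisation day is stated. If the envelope were opened on day 1 itself, the check would still be described within the allocated arm.

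**2. The planned number.** Inputs from 5.2 and 5.1 (Statistical analysis): p1 = 0.099, p2 = 0.184, two-sided 5% level, 80% power, 1:1.

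n per arm = (1.960 + 0.842)² × [p1(1 − p1) + p2(1 − p2)] / (p2 − p1)²
= 7.849 × (0.0892 + 0.1501) / 0.085² = 260.01, rounded up to **261**, so 522 in total. The protocol's figure reproduces.

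Power with 261 per arm (pooled variance under the null):
- mean rate = 0.1415
- standard error under the null = √(0.1415 × 0.8585 × 2/261) = 0.03051
- standard error under the alternative = √((0.0892 + 0.1501)/261) = 0.03028
- z = (0.085 − 1.960 × 0.03051)/0.03028 = 0.832, so power = **79.7%**

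**3. Effect of an assumed loss before start.** The documents give no rate, so every loss below is an assumption. It is also assumed that the planning rates exclude the women lost.

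*Equal loss d in both arms.* If non-starters count as non-events, both rates are multiplied by (1 − d). If they are left out, n is multiplied by (1 − d).

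| Assumed loss | Rates if kept | Power if kept | n per arm if left out | Power if left out |
|---|---|---|---|---|
| 2% | 9.70% vs 18.03% | 78.8% | 255.8 | 78.9% |
| 5% | 9.41% vs 17.48% | 77.3% | 248.0 | 77.7% |
| 10% | 8.91% vs 16.56% | 74.7% | 234.9 | 75.4% |
| 20% | 7.92% vs 14.72% | 69.0% | 208.8 | 70.4% |

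*Unequal loss, all randomised women analysed, 261 per arm.*

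| Assumed loss | Rates NC vs HRT | Difference | Power |
|---|---|---|---|
| 5% in HRT only | 9.90% vs 17.48% | 7.58 points | 71.3% |
| 10% in HRT only | 9.90% vs 16.56% | 6.66 points | 61.3% |
| 10% in NC only | 8.91% vs 18.40% | 9.49 points | 88.7% |

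The last row is no advantage. The difference grows from 8.5 to 9.49 points only because women in one arm did not start.

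**The case against.** Several points on the other side carry weight.

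- **The timing is not fixed to a day.** Consent is an inclusion criterion and can first be signed on day 1 of the next cycle. Taken with the rule in 4.4, allocation on day 1 is a possible reading, and it leaves almost no gap before the check. This stands as a limit on the concern. It does not remove it, because 4.3 also allows signature at transfer and 4.5 still places the check inside each arm.
- **A reader might infer that non-basal women leave the trial.** The text does not say so. In NC it even provides for an earlier examination depending on the values. A later start with the allocation kept fits the silence equally well.
- **A reader might infer that the stated 80% power, or the 522, is wrong.** It is not: the number follows from the stated inputs. A started cycle is undefined. If it means day 1 of the cycle, women who fail the check are already inside the 9.9% and 18.4%, and only women lost before day 1 would be extra.
- **The losses are hypothetical.** Eligibility requires regular cycles of 24-35 days and excludes oligo-amenorrhea. Nothing in the documents supports a loss as high as 20%, or any particular imbalance between arms. At 2% the effect on power is about one percentage point.
- **Who is analysed may be settled in an analysis plan not shown.** That is accepted, and the absence of such a rule is not part of this point. The time of allocation remains a protocol matter.

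**Conclusion.** The point holds as a cheap improvement to the design, not as an error in the sample size. As written, the day 1-2 check is made after open-label allocation and has different consequences in the two arms, and consent may follow allocation. Both leave room for loss that depends on the arm.

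Its size cannot be determined from the documents. Under equal losses of 2% to 10% counted as non-events, power falls from 79.7% to between about 79% and 75%, a modest cost. Unequal loss would matter more, since it moves the estimated difference itself: 5% in HRT only would give about 71%. These figures rest on assumed loss rates and on the planning rates excluding the women lost. They show what the present order could cost, not what it will cost.

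**What to change.** - **4.3 and 4.4:** require signed consent before randomisation and delete the option to sign at transfer. Moving the envelope alone would not be enough, because a woman could still learn her arm before signing.
- **4.3 and 4.4:** have the study nurse open the envelope on day 1 or 2 of the FET cycle, once eligibility is confirmed and the already scheduled hormone result has been judged basal, by the centre's usual standard and without knowledge of the arm.
- **4.2:** add that result as a condition for randomisation. A woman who is not basal is not randomised and may be re-screened.

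**Cost.** No extra visit or blood test is needed, since both arms already have them, and 522 need not change on this account. Women would learn their arm later. The result, the envelope and the arm-specific start would all have to be handled within days 1-2, which takes some organisation at the centre.

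**What it does not solve.** Cancellations later in the cycle, such as for inadequate endometrium in the HRT arm, would still occur after randomisation.

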[figure not shown]
2. Study Flowchart and Design

Group A: NC (awaiting spontaneous LH surge)

Group B: HRT¹

¹ Progesterone supplementation is started when the endometrium is considered adequate after E2 administration. E2 supplementation vary between 1 to 3 weeks depending on the adequate proliferation of the endometrium.

Legend: B: serum hormone analysis (estradiol (E2), P, LH, follicle stimulation hormone (FSH));
US: ultrasound scan; P: progesterone

3. Study objectives and endpoints

The aim of the current RCT is to compare miscarriage rates (before 8 weeks) between true NC (awaiting spontaneous LH surge) and HRT FET cycles in PGT patients, with biopsy on day 5 of embryonic development. The advantage of performing the study in PGT patients is the exclusion of aneuploidy as a cause of miscarriage.

3.1 Primary outcome:

Miscarriage rate before 8 weeks of gestation, defined as a spontaneous loss of a clinical pregnancy before 8 weeks of gestational age, in which the embryo(s) is/are nonviable and is/are (not) spontaneously absorbed or expelled from the uterus (Zegers-Hochschild et al 2017).

3.2 Secondary outcomes:

Miscarriage rate after 8 weeks of gestation, defined as a spontaneous loss of a clinical pregnancy after 8 weeks but before 22 completed weeks of gestational age, in which the embryo(s) or fetus(es) is/are nonviable and is/are not spontaneously absorbed or expelled from the uterus (Zegers-Hochschild et al 2017).

Clinical pregnancy defined as a pregnancy diagnosed by ultrasonographic visualization of one or more gestational sacs or definitive clinical signs of pregnancy. In addition to intra-uterine pregnancy, it includes a clinically documented ectopic pregnancy (Zegers-Hochschild et al 2017).

Ongoing pregnancy rate defined as the number of pregnancies after 20 weeks of gestation.

4. Methodology

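### Consent may be signed as late as embryo transfer, after randomisation and open-label preparation, although signed consent is an inclusion criterion for randomisation

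*Protocol*

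**What the plan says.** - Section 4.2 lists "Signed informed consent" among the inclusion criteria.
- Section 4.3 places allocation after the fresh cycle, if non-affected embryos are available: "Patients willing to participate and fulfilling the inclusion criteria will be randomized to one of the two treatment arms following the fresh ICSI cycle".
- Section 4.4 repeats the condition: "patients will only be randomized if they meet the complete eligibility criteria".
- The sentence in 4.3 that dates the signature reads: "Informed consent forms will be signed either on the first day of the following menstrual cycle or on the moment of frozen-warmed embryo transfer".
- Section 4.1 states: "The current study will be an open label randomized trial".

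The only steps described before allocation are that the physician informs the patient at the first consultation and that she is willing to take part. No earlier signature is mentioned.

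**The concern.** If the form is signed at transfer, the woman has already been randomised and has gone through natural-cycle monitoring or hormone replacement. She entered the trial without meeting one of its inclusion criteria, and site staff who use this option cannot comply with 4.2, 4.3 and 4.4 together.

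Two things are at stake. The first is direct: an informed but unsigned woman can follow a randomly assigned regimen up to transfer.

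The second is an inference, because the protocol does not say how unsigned women are handled. A woman whose cycle stops before transfer, or who declines once she knows her arm, may never sign. If unsigned women are then left out, the analysable set may depend on the arm and depart from the per-started-cycle basis of the planning rates in section 5.2.

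**Working it through.** **Order of events.** Setting the sections side by side:

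1. Signed consent is an inclusion criterion (4.2).
2. Randomisation requires all criteria to be met (4.3, 4.4). Signature must therefore precede randomisation.
3. The arms share a blood sample on cycle day 1 or 2 and separate after its result (4.5). In the HRT arm: "If these values are considered basal for the beginning of the follicular phase, estrogen supplementation" is started, and later "embryo transfer is scheduled on the sixth day of progesterone". In the natural-cycle arm, transfer follows six days after the LH surge. Randomisation must therefore precede the preparation, and the preparation precedes transfer.
4. Signature at transfer (4.3) thus comes after randomisation, which contradicts step 2.
5. Signature on day 1 can satisfy step 2. Randomisation is dated only as after the fresh ICSI cycle, so the envelope could be opened after signature. The text does not say that it is.

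**Medication before a signature at transfer, HRT arm.** I count five full days of progesterone before transfer on the sixth day. The estradiol duration differs between the flowchart note in section 2 ("E2 supplementation vary between 1 to 3 weeks depending on the adequate proliferation of the endometrium") and sections 4.5 and 5 (check after 10 to 14 days, with up to 14 more allowed in 4.5), so both are shown.

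| Source of estradiol duration | Shortest | Longest |
|---|---|---|
| Section 2 | 7 + 5 = 12 days | 21 + 5 = 26 days |
| Section 4.5 | 10 + 5 = 15 days | 14 + 14 + 5 = 33 days |

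Escape ovulation can alter these figures.

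**The plan's own sample size.** Inputs from sections 5.1 and 5.2: 9.9% against 18.4%, two-sided 5%, 80% power. With unpooled variance, n per arm = (1.960 + 0.842)² × [0.099 × 0.901 + 0.184 × 0.816] / 0.085² = 7.849 × 0.2393 / 0.007225 = 260.01, rounded up to 261, or 522 in total. The stated figure is reproduced. No allowance for losses is stated.

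**Illustration of selection.** The documents give no loss rates, so those below are assumptions. I took 261 randomised per arm, n = 261 × (1 − loss) rounded, and exact enumeration of two binomials under the uncorrected two-sided 5% chi-squared test. For the false-positive rate, both arms have the same true rate p = (9.9% + 18.4%) / 2 = 14.15%. The observed rate among women retained is

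- p / (1 − loss) if all lost women are event-free, as fits cycles stopped before transfer;
- p × (1 − 0.5 × loss) / (1 − loss) if half are event-free and half have the average rate;
- p if losses are unrelated to outcome, as is possible for women who decline after learning their arm.

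| Assumed loss, one arm / other arm | n | All event-free | Half event-free | Unrelated |
|---|---|---|---|---|
| 5% / 5% | 248 / 248 | 5.0% | 5.0% | 5.0% |
| 5% / 10% | 248 / 235 | 5.8% | 5.2% | 5.0% |
| 5% / 15% | 248 / 222 | 8.1% | 5.7% | 4.9% |
| 5% / 20% | 248 / 209 | 12.1% | 6.7% | 4.9% |

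At 5% / 20% with all lost women event-free, for example, the retained rates are 0.1415 / 0.95 = 14.9% and 0.1415 / 0.80 = 17.7%, although the true rates are equal.

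**Power at 9.9% against 18.4%, same exact method.** Without loss, 80.5%. With equal losses of 10% (235 per arm) or 20% (209 per arm), it is 76.1% or 70.9% if losses are unrelated to outcome, and 81.1% or 81.9% if all lost women are event-free.

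**The case against.** The best defence accepts the contradiction and disputes its weight.

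- **Women are informed and willing before allocation, and the HRT regimen is the centre's local protocol.** This is true and it tempers the exposure argument. Willingness is still not the signature that 4.2 requires, and 4.3 names willingness and meeting the criteria as separate conditions.
- **The bias argument is conditional.** It needs late signing to be used, unsigned women to be excluded, and losses that differ by arm and relate to outcome. The protocol states none of these, and the analysis set may be defined in an SAP that is not at hand. This stands. So does the point that regular cycles are an inclusion criterion and that escape ovulation still leads to transfer, both of which limit losses before transfer. Cancellation for a thin endometrium is described only for the HRT arm, and only after prolonged priming.
- **The 12.1% is an extreme case.** It needs 20% against 5% loss with every lost woman event-free. It is an illustration and not an estimate.
- **Day-1 signing can be compliant.** Agreed. The missing order of signature and envelope is a point to clarify and adds nothing to the seriousness.

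None of this removes the conflict for the transfer option.

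**Conclusion.** The concern holds. The option to sign at embryo transfer cannot be reconciled with 4.2 and 4.4, and the current text shows this without any assumption. It must be corrected, because following the rule as written means allocating and treating women who have not signed. That conclusion rests on the order of consent and eligibility alone.

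The statistical consequence is secondary and of unknown size and direction. Under the assumed losses above it ranges from no effect to a clearly inflated error rate.

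**What to change.** - In 4.3, delete the embryo-transfer option and replace the consent sentence with: *Written informed consent is signed before the randomisation envelope is opened.* Signature at the first consultation meets this. So does signature on day 1, provided the envelope is opened only afterwards.
- In 4.4, add that the study nurse opens the envelope only after seeing the signed form. The nurses already hold that task.
- Check that 4.2, 4.3 and 4.4 then agree. The definition of the analysis set may be left to the SAP.

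The cost is amendment wording; the sample size is unchanged. Consent at the first consultation produces some forms from women who later have no non-affected embryo. Consent on day 1 means that signature and envelope opening must both fit in before the arms separate on day 1 or 2.
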